5.0 STATISTICAL ANALYSIS

5.1 Subject numbers.

5.1.1 Sample size.

For this observational, retrospective study, we propose a sample size of 5000 patients. Given the descriptive nature of this study no formal hypothesis testing is required. We will be retrospectively including patients fulfilling eligibility criteria between 1st January 2020 and 1st of April 2020.

5.2 Statistical methods.

Analysis of overall survival (OS) will validate the prognostic value of each clinico-pathologic trait collected at treatment initiation. Univariable analysis of survival will be used to derive median OS and associated 95% CI by using Kaplan-Meier methods and Log-rank tests.

The HRs and their associated CIs for OS will be computed using unadjusted and adjusted Cox proportional hazards models. We will employ a backward stepwise conditional model where each variable with an entry threshold of $p<0.05$ and an exit threshold of $p<0.10$ at each iteration. Proportional hazards will be adjusted for factors including active anticancer treatment type and features reflective of SARS-CoV-2 infection. Receiver-operating characteristics curve (ROC) will be used to test each variable for the accuracy of prediction of mortality at landmark survival endpoints (ie. 8, 12 weeks).

To test the predictive accuracy of each candidate prognostic variable we will use Harrell's rms packages to identify a subset of predictors by backward elimination, estimating the confidence intervals of the c-index statistics via bootstrapping (150 iterations).

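### Adjusted hazard ratios are reported only for variables that survive backward elimination in the same patients, so the reported set of intervals falls below nominal coverage and weak effects are overstated when deaths are few

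*Combined protocol and SAP*

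**What the plan says.** Section 5.2 opens by saying that the survival analysis "will validate the prognostic value of each clinico-pathologic trait". It then states that "The HRs and their associated CIs for OS will be computed using unadjusted and adjusted Cox proportional hazards models". The next sentence gives the selection rule: "We will employ a backward stepwise conditional model", with entry at p<0.05 and "an exit threshold of $p<0.10$ at each iteration".

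On adjustment, the section adds: "Proportional hazards will be adjusted for factors including active anticancer treatment type and features reflective of SARS-CoV-2 infection". It does not say that these factors are exempt from elimination, and the list is left open.

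The only resampling planned is for discrimination: "estimating the confidence intervals of the c-index statistics via bootstrapping (150 iterations". It does not apply to the HRs or their intervals. A 95% level is written only for the Kaplan-Meier medians ("Univariable analysis of survival will be used to derive median OS and associated 95% CI by using Kaplan-Meier methods and Log-rank tests"); no level is given for the HR intervals.

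Section 3.2 describes one database. No hold-out set or validation cohort is mentioned. Section 3.1 makes the evaluation of prognostic factors for survival the second endpoint.

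**The concern.** Ordinary Cox intervals treat the variables in the model as fixed in advance. Here the same data choose them. A variable with no effect stays in only if its estimate happens to be extreme. A variable with a weak effect stays in mainly when it is overestimated. The plan describes no shrinkage, no post-selection interval and no prespecified full model to offset this.

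At stake is the answer to the second endpoint. The adjusted HR table would show a filtered set of estimates with intervals that take no account of the filter. Traits that were removed would have no adjusted estimate, although section 5.2 speaks of each trait. Selection and estimation in a single cohort also cannot validate a prognostic factor in the usual sense.

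**Working it through.** **Inputs from the plan.** Retention at p<0.10, i.e. |Z|>1.645 (section 5.2); one database (3.2); up to 5000 patients (4.1, 5.1.1). The plan gives no expected number of deaths, no count of model candidates, no effect sizes and no coverage figure, so there is nothing of its own to reproduce. Everything else below is an assumption.

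**Step 1: a single null variable.** It is retained if |Z|>1.645 (probability 0.10). Its 95% interval misses the truth if |Z|>1.96 (probability 0.05). Coverage given retention = 1 − 0.05/0.10 = 50%. The number of patients does not enter.

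**Step 2: a single real effect.** Let D be deaths, q the prevalence and d = ln(HR) × √(D·q(1−q)), with Z ~ N(d,1).
- Coverage given retention = P(|Z−d|<1.96 and |Z|>1.645) / P(|Z|>1.645).
- Inflation of the log HR = E[Z | retained] / d.

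| d | Coverage | Inflation of log HR |
|---|---|---|
| 0.5 | 71% | 3.35 |
| 1 | 89% | 2.18 |
| 2 | 96% | 1.29 |
| 3 | 97% | 1.06 |
| 5 | 95% | 1.00 |

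For HR 1.20 (ln = 0.182) and q = 0.5:
- 100 deaths: d = 0.182 × √25 = 0.91, inflation 2.34, mean retained HR = exp(0.182 × 2.34) = 1.53.
- 300 deaths: d = 1.58, inflation 1.53, mean retained HR 1.32.
- 1500 deaths: d = 3.53, inflation 1.02, mean retained HR 1.20.

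**Step 3: joint elimination, normal-theory simulation.** Assumed: 24 binary candidates, prevalence 50%, pairwise correlation 0.2; two with HR 2.0, six with HR 1.2, sixteen null. The full-model estimates are drawn from N(β, V), with V the inverse of D × 0.25 × the correlation matrix. The weakest variable is removed and the rest re-estimated until all have |Z|≥1.645.

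| Quantity | 100 deaths | 300 deaths | 1500 deaths |
|---|---|---|---|
| Coverage, all retained HRs | 75% | 80–81% | 88% |
| Mean reported HR when the truth is 1.20 | 1.60 | 1.35 | 1.21 |
| Retained SE / full-model SE | 0.96 | 0.97 | 0.98 |
| Null variables with interval excluding 1, stepwise | 0.93 | 0.94 | 0.86 |
| The same, full model | 0.78 | 0.81 | 0.79 |

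About 1.7 nulls are retained per analysis, with coverage of 43–49%, in line with step 1. Coverage for HR 2.0 is 94–96% throughout; for HR 1.2 it is 97% at 1500 deaths.

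**Step 4: Cox models fitted to simulated survival data, different assumptions.** Twenty correlated binary candidates (prevalence 0.3, latent correlation 0.3); HRs of 2.0 (one), 1.5 (one), 1.2 (two), 1.1 (four) and 1.0 (twelve); about 24% deaths.
- N=1000 (about 244 deaths): coverage of retained intervals 76% overall and 44% for nulls; a true 1.2 is reported as 1.40.
- N=5000 (about 1217 deaths): 86% overall and 47% for nulls; a true 1.2 is reported as 1.22.

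The overall figure at N=5000 can be rebuilt from retention × coverage by class:
- Variables retained per run: 1.000 + 1.000 + 2×0.910 + 4×0.480 + 12×0.101 = 6.952.
- Of these, covered: 1.000×0.944 + 1.000×0.948 + 1.820×0.960 + 1.920×0.935 + 1.212×0.469 = 6.003.
- Ratio: 6.003/6.952 = 86%.

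The full 20-variable model on the same data gave 94–96% coverage for every true HR and essentially unbiased estimates.

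**The case against.** A reader might infer that all the planned intervals are too narrow, or that the table would fill with false prognostic factors. Neither follows. Retained standard errors are only 2–4% smaller than those of the full model. Null variables whose interval excludes 1 number 0.86–0.94 per analysis with elimination and 0.78–0.81 without, a difference of roughly 0.1. The low coverage among retained nulls arises largely because nulls whose intervals correctly include 1 are dropped from view. Strong predictors are unaffected, and moderately strong ones slightly exceed 95%. This part of the objection stands and limits the point.

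Other arguments stand in part:
- The sizes depend on assumed effects and deaths. Section 1.1 gives prior reason to expect effects of age, heart disease, lung disease and diabetes, so the share of nulls may be smaller than assumed. With 5000 patients and about 24% deaths, inflation at HR 1.2 is trivial. However, 5000 is an upper aim, the Synopsis lists one centre, section 5.1.1 gives a three-month inclusion window, and no number of deaths is stated. Small event counts cannot be ruled out.
- The sentence on adjustment factors could mean that they are forced in. Forced factors would escape direct retention bias, but the text does not say so.
- Unadjusted HRs, if reported for every variable, are unaffected.
- The study is called descriptive and no decision rule rests on these HRs. That lowers the severity, but evaluating prognostic factors is still a named endpoint.

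**Conclusion.** The point holds as a should-fix. Reading adjusted HRs and intervals from a p-value-selected model, without correction, puts the reported set of intervals below its nominal level: about 75–88% over 100 to 1500 deaths under the 24-candidate assumptions, and 76–86% in the separate Cox simulation. For retained null variables coverage is about 44–50%, and more patients do not cure it. Overstatement of weak effects is material at 100 to 300 deaths and nearly gone at 1500.

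The direction for null and weak variables follows from the selection rule. The sizes rest on the assumed effects, correlation, prevalence and deaths, and on a 95% level that the plan does not state for HRs. The documents do not support the broader claim that every interval is invalid. The fault is selective reporting of extreme estimates, together with the lack of an adjusted HR for each eliminated trait.

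**What to change.** In section 5.2:
- Name the candidate list and report adjusted HRs with 95% intervals for all of it, from one prespecified full Cox model with no removal on p-values. If deaths are few for the number of parameters, shorten the list without reference to outcome, or use a penalised Cox model and state how its intervals are obtained.
- Keep backward elimination for the prediction model only. Label any HRs and intervals taken from that model as exploratory and not corrected for selection.
- Replace *validate* with *estimate* in the opening sentence.

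The cost is a wording change and one model fit, with slightly wider intervals and a longer table. No new data are needed. The change should be made before outcomes are analysed.

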RESEARCH STUDY PROTOCOL

Title:	OnCovid: natural history and outcomes of cancer patients during the COVID19 epidemic.
Protocol Version:	Version 3.0 dated 1st June 2020
Chief Investigator:	[name] [name]
Sponsor:	Imperial College London
IRAS Project ID:	282140

SYNOPSIS

Study title: OnCovid19: natural history and outcomes of cancer patients during the COVID19 epidemic.

Objectives: To describe the natural history and clinical outcomes of patients with cancer and Covid19 infection.

Study design & methodology: Retrospective observational study.

Research will be limited to secondary use of information previously collected in the course of normal care (without an intention to use it for research at the time of collection). Every aspect of this research will be undertaken by staff within a care team using information previously collected in the course of care for their own patients.

Routinely collected clinical data including patients' demographics, prior medical history, cancer history including prior and current anti-cancer therapy, co-morbidities will be collected in a data collection proforma. Results of routinely collected blood tests, radiologic assessment and therapies received by the patient will also be entered onto the database. Clinical outcomes including response to treatment and patients' survival will be evaluated in relationship to baseline clinico-pathologic profile.

Duration of Research: 2 years

Planned sample size:

Due to the descriptive and retrospective nature of this study, no sample size is required for hypothesis testing. We aim to describe clinical outcomes of consecutively presenting patients with a diagnosis of cancer and SARS-CoV-2 infection and aim to retrieve data on up to 5000 fulfilling eligibility criteria.

**Summary of
eligibility
criteria:** Inclusion criteria:

1. Be ≥ 18 years of age.
2. Have a confirmed diagnosis of malignancy of any type.
3. Have a confirmed diagnosis of SARS-CoV-2 infection.

**Number of study
centres:** 1

Endpoints: To retrospectively describe the survival of cancer patients affected by SARS-CoV-2 infection.

General Study Information

Name of sponsor: **Imperial College London**
Joint Research Compliance Office
[name]
Medical School Building
St Mary's Campus
[name]
[name]

Contact: [name]
Research Governance Manager
Email: [contact]
[contact]

Principal investigator: **[name] [name]**
Clinical Senior Lecturer and Consultant in Medical Oncology
Imperial College London

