3.2 Methods

Patients with a diagnosis of malignancy and SARS-CoV-2 infection will be identified from electronic medical records and entered into a pre-designed database.

Methodologically, this project will be limited to secondary use of information previously collected in the course of normal care (without an intention to use it for research at the time of collection). Every aspect of this project will be undertaken by staff within a care team using information previously collected in the course of care for their own patients.

Routinely collected clinical information including patients' demographics, prior medical history, cancer history including prior and current anti-cancer therapy, co-morbidities will be collected in a data collection proforma. Results of routinely collected blood tests, radiologic assessments and therapies received by the patient will also be entered onto the database. Clinical outcomes including response to treatment and patients' survival will be evaluated in relationship to baseline clinico-pathologic profile. Clinico-pathologic will be correlated to patient's outcome, in particular overall survival (OS) as derived from electronic medical records.

The database consists of a Microsoft Excel spreadsheet including the following variables: age, gender, smoking status, prior comorbidities (cardiovascular, diabetes, dementia, pulmonary and kidney disease, liver disease, hypertension, immunosuppression), histotype of malignancy, date of first cancer diagnosis and stage of cancer at the time of SARS-CoV-2 infection, prior and current anti-cancer therapy, presenting symptoms at SARS-CoV-2 diagnosis and severity, routine blood tests at SARS-CoV-2 diagnosis (routine biochemistry, full blood count), radiologic data at diagnosis and follow up data (admission to intensive care, anti SARS-CoV-2-specific therapy, complications from SARS-CoV-2 infection).

Data collection will be completely solely by members of the patients' team. Resulting clinical data will be fully anonymised and stored in a password-protected NHS computer.

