4.0 SUBJECT POPULATION

4.1 Subject number and selection

We plan to collect descriptive data in all consecutive patients with confirmed diagnosis of SARS-CoV-2 infection and cancer. Due to the descriptive and retrospective nature of this study, no sample size is required for hypothesis testing. We aim to describe clinical outcomes of consecutively presenting patients with a diagnosis of cancer and SARS-CoV-2 infection and aim to retrieve data on up to 5000 fulfilling eligibility criteria.

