4.1.2 Exclusion criteria

Patients will not be entered in the study database when one or more of the following CRITERIA are present:

1. Unconfirmed diagnosis of SARS-CoV-2 infection
2. Insufficient clinical/follow up data.

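### Applied to short follow-up, the data exclusion overstates mortality; if such patients are entered instead, the 8- and 12-week ROC has no rule for those last seen alive before the landmark

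*Combined protocol and SAP*

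**What the plan says.** Section 4.1.2 states: "Patients will not be entered in the study database when one or more of the following CRITERIA are present". The second criterion listed is "Insufficient clinical/follow up data". No minimum follow-up is given, and the section does not say whether the criterion concerns baseline records, outcome records or length of observation.

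Section 3.2 takes "overall survival (OS) as derived from electronic medical records". No vital-status check or data cut-off is described. The synopsis endpoint is "To retrospectively describe the survival of cancer patients affected by SARS-CoV-2 infection", and Section 3.1 adds prognostic factors for survival.

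Section 5.2 plans Kaplan-Meier, log-rank, Cox and c-index analyses, all of which can use a patient censored at last contact. It also plans an ROC curve, which "will be used to test each variable for the accuracy of prediction of mortality at landmark survival endpoints (ie. 8, 12 weeks". It does not say how that step treats a patient whose status at 8 or 12 weeks is unknown.

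**The concern.** A patient who dies before a landmark has complete follow-up by definition. A rule that removes people for short follow-up can therefore remove only patients last known alive. The rule acts at entry to the database, so neither censoring nor weighting can bring those patients back, and every survival analysis inherits the selection. The first quantity at stake is the one the synopsis names, survival itself. A larger sample does not reduce the error.

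If these patients are entered, Kaplan-Meier and Cox can handle them. An ROC at a fixed time needs each patient labelled dead or alive, and a patient last seen alive at week 5 has no label at week 8 or 12. The analyst must then choose a treatment after seeing the data. The two obvious choices, dropping these patients or calling them alive, move the AUC in opposite directions when follow-up differs by trait.

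**Working it through.** The plan has no mortality, loss or AUC figure to reproduce, and its 5000 is a target without a derivation. The sizes below therefore rest on assumed inputs.

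**Inputs.** From the documents: landmarks at 8 and 12 weeks (Section 5.2), and up to 5000 patients (synopsis and Section 4.1; Section 5.1.1 states 5000). Assumed: exponential survival with 30% mortality at 12 weeks; a share f of patients followed to 12 weeks; the rest lost uniformly over weeks 2 to 12; a binary trait with 50% prevalence and no prognostic value (true AUC 0.50, true HR 1.0).

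**Step 1: death before loss.** The rate is −ln(0.7)/12 = 0.02972 per week. Averaging 1 − exp(−0.02972c) over c from 2 to 12 gives 0.185. Hence observed deaths are d = 0.3f + 0.185(1 − f), and known 12-week survivors are a = 0.7f.

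**Step 2: everyone censored before 12 weeks is excluded.** Apparent mortality is d/(d + a). No censoring before week 12 remains, so Kaplan-Meier gives the same value. Coverage is that of a 95% interval for the true 30%, with n counted as patients entered.

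| f | d | a | Apparent mortality | Coverage, n=1000 | Coverage, n=5000 |
|---|---|---|---|---|---|
| 0.95 | 0.2942 | 0.6650 | 30.7% | 93% | 83% |
| 0.90 | 0.2885 | 0.6300 | 31.4% | 85% | 43% |
| 0.80 | 0.2770 | 0.5600 | 33.1% | 46% | 0.3% |

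- With the same patients retained and censored (f = 0.80), simulated Kaplan-Meier coverage was about 95% at both sizes.
- With f = 0.80, a true 15% becomes 16.9% and a true 45% becomes 48.7%.
- If instead every death by the landmark is recorded and a share c of survivors is dropped, apparent mortality is m/(m + (1 − m)(1 − c)). For m = 0.30 and c = 0.10 this is 0.30/(0.30 + 0.63) = 32.3%. It is higher than 31.4% because no deaths are lost.

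Loss that differs by trait also distorts comparisons. At f = 0.75, mortality is 0.2712/(0.2712 + 0.5250) = 34.06%. With 90% vs 75% complete, the null HR becomes ln(1 − 0.3141)/ln(1 − 0.3406) = 0.905. With 95% vs 90%, it is ln(1 − 0.3067)/ln(1 − 0.3141) = 0.97. For 90% vs 75%, simulation gave a Cox HR of 0.898 (0.996 if retained) and a c-index of 0.486 (0.499 if retained). The log-rank test rejected in 50% of datasets at n=5000 and 14% at n=1000, against about 5% if retained.

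**Step 3: short follow-up is entered and the ROC must class it.** For a binary trait, AUC = 0.5 + 0.5(share of deaths with the trait − share of survivors with the trait).

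- 90% vs 75%: the share among deaths is 0.2885/(0.2885 + 0.2712) = 0.5154. With unknowns dropped, the share among survivors is 0.630/(0.630 + 0.525) = 0.5455, so AUC = 0.485. With unknowns called alive, it is 0.7115/(0.7115 + 0.7288) = 0.4940, so AUC = 0.511.
- 95% vs 90%: the share among deaths is 0.5049; among survivors it is 0.5135 (dropped) or 0.4980 (alive). AUC is 0.496 or 0.503.
- 95% vs 60%, an extreme case: 0.46 or 0.53.
- Equal follow-up: 0.50 either way.
- At 8 weeks with 90% vs 75%: 0.492 or 0.505.

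At 12 weeks, the simulated 95% CI excluded 0.50 in 45% (dropped) or 28% (alive) of datasets at n=5000 for 90% vs 75%, and in 13% or 9% at n=1000. For 95% vs 90% the rates were about 8% or 7% at n=5000 and about 6% at n=1000. The nominal rate is 5%.

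**Step 4: cross-check with a prognostic marker.** A separate Weibull simulation at 8 weeks had 33% mortality, a true AUC of 0.717, and 16% to 36% of patients unclassifiable. Dropping them gave an AUC of about 0.72 when censoring was unrelated to the marker, 0.69 to 0.66 when higher-risk patients were followed longer, and 0.74 to 0.76 when they were lost sooner. Dropping raised apparent mortality in every case (36% to 46%).

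**The case against.** The strongest reply is that the exclusion may mean no usable record or no outcome data at all. Section 4.1.2 sets no 12-week minimum, and the larger figures in Step 2 exist only under the short-follow-up reading. That stands: the selection is a risk created by the wording and not an established fact. The milder inputs are also nearly harmless, 5000 is an upper limit, and no formal hypothesis testing is planned, so a CI that excludes 0.50 is a gauge and not a decision rule.

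A reader might infer more than the documents support:

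- *That both harms apply in full together.* If everyone censored before 12 weeks is excluded, every entered patient has a known status and the ROC can class them all. If nobody is excluded for short follow-up, only the ROC gap remains. A cut-off in between would give some of each.
- *That the exclusion contradicts consecutive enrolment.* Section 4.1 says "We plan to collect descriptive data in all consecutive patients with confirmed diagnosis of SARS-CoV-2 infection and cancer", but it goes on to limit the aim to patients who meet the eligibility criteria, and the exclusion is one of those criteria.
- *That an ordinary ROC has been chosen.* Section 5.2 names no type of ROC. What can be said is that the handling of unknown status is not stated.
- *That the removed patients are all survivors.* They are patients last known alive. In the model above, (0.300 − 0.185)/(1 − 0.185) = 14% of them die by week 12.
- *That the calendar leaves too little follow-up.* Section 5.1.1 describes "retrospectively including patients fulfilling eligibility criteria between 1st January 2020 and 1st of April 2020", and the synopsis gives "Duration of Research: 2 years". Later extraction within that period removes administrative censoring before 12 weeks. Loss of contact in the records is what remains.

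The defence that the study is descriptive does not answer the point. An overstated mortality is a descriptive error, and Section 5.2 also sets out to validate prognostic value.

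**Conclusion.** The concern holds in conditional form, and the plan should be changed. Applied to short follow-up, the exclusion overstates mortality even when loss is unrelated to any trait, and it can bias Kaplan-Meier, Cox and c-index results beyond later repair. If it is not applied that way, the landmark ROC lacks a rule for unknown status. That second harm is minor: near zero when loss is unrelated to the trait, and for a null trait a shift of 0.003 to 0.015 at 12 weeks across the 95% vs 90% and 90% vs 75% cases. It grows with heavier, marker-dependent loss. The mortality error is 0.7 to 3.1 percentage points for 95% to 80% complete follow-up at an assumed 30% mortality. The directions follow from the logic of the design. The sizes rest entirely on assumed mortality and loss, because the documents give neither. If status is known for every patient at both landmarks, an ordinary ROC is valid.

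**What to change.** 1. In Section 4.1.2, limit the exclusion to missing eligibility or essential baseline data. Enter patients with short follow-up, censor them at last contact, and report how many are excluded and why. This has to come first, because no weighting recovers patients who were never entered.
2. In Section 5.2, for 8 and 12 weeks, either confirm vital status for all patients from the records and use an ordinary ROC, or use a time-dependent ROC with inverse-probability-of-censoring weights. The weights should be conditional on the trait and on recorded predictors of follow-up. In the 90% vs 75% case, pooled weights left the AUC at 0.485, while trait-conditional weights gave 0.499.
3. Report the number with unknown status at each landmark, by trait. This would show whether the problem exists in practice.

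The cost is the wording of one criterion and one analysis sentence, plus a little extra analysis. The weighted ROC relies on a censoring model, which cannot correct loss driven by unrecorded factors.

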4.1.1 Inclusion criteria

The investigators will evaluate and include consecutive patients observed in the outpatients and inpatients facility of the study centre meeting all the following CRITERIA:

Inclusion criteria:

1. Be ≥ 18 years of age.
2. Have a confirmed diagnosis of malignancy of any type.
3. Have a confirmed diagnosis of SARS-CoV-2 infection.

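### Section 5.2 states no optimism correction for the c-index of a model chosen by backward elimination, and does not say whether the hazard ratios come from that same model

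*Combined protocol and SAP*

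**What the plan says.** Section 5.2 describes variable selection in two consecutive paragraphs.

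- The first specifies a backward stepwise conditional Cox model with entry at p<0.05 and exit at p<0.10. It adds: "Proportional hazards will be adjusted for factors including active anticancer treatment type and features reflective of SARS-CoV-2 infection".
- The second opens "To test the predictive accuracy of each candidate prognostic variable" and uses rms to "identify a subset of predictors by backward elimination, estimating the confidence intervals of the c-index statistics via bootstrapping (150 iterations"). It gives no stopping rule and does not refer back to the stepwise model.

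The section opens by saying that the survival analysis will validate prognostic value. No section mentions a validation cohort, a data split, an optimism correction, or repeating the selection within resamples.

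On cohort size, section 5.1.1 says "we propose a sample size of 5000 patients", included "between 1st January 2020 and 1st of April 2020". Section 4.1 words it as a ceiling: "aim to retrieve data on up to 5000 fulfilling eligibility criteria". Section 4.1.1 draws on "consecutive patients observed in the outpatients and inpatients facility of the study centre", and the synopsis gives one centre. Section 4.1.2 excludes patients with insufficient data. Section 7.5, however, speaks of NHS trusts in the plural. No number of deaths, death rate or count of candidate parameters is stated.

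**The concern.** Backward elimination keeps the variables that happen to fit the sample best. A c-index computed on that sample credits the model with chance associations as well as real ones. A bootstrap used only for a confidence interval leaves this bias in place and puts the interval around a figure that is too high.

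Endpoint 2 in section 3.1 is to evaluate prognostic factors for survival, so readers will use the c-index to judge how well the selected factors discriminate.

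A second uncertainty is added by the unclear relation between the two paragraphs. If they are separate eliminations, the adjusted hazard ratios and the c-index may belong to different models.

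**Working it through.** **Inputs.** The 5000 is given without a death rate, effect size or precision target, so there is no figure to reproduce. Section 3.2 lists about 21 baseline items: 3 demographic or smoking, 8 comorbidities, 3 cancer descriptors, 2 for prior and current therapy, 2 for symptoms and severity, 2 blood panels, 1 radiology. Several carry more than one parameter. Assumptions: 25 or 50 candidate parameters; 10%, 20% or 35% deaths; 6 truly prognostic variables; c-index of the true model about 0.71-0.72 (moderate signal) or 0.61 (weak).

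**Step 1: size of the overstatement.** Optimism = c-index on the development data minus c-index of the same fitted model in new patients. Each simulated cohort had Wald backward elimination at p 0.10, and the fitted model was then evaluated in 20,000 new patients (60-120 runs per cell). Two cells with 25 candidates and 20% deaths: at N=500, 0.736 - 0.691 = 0.045; at N=5000, 0.717 - 0.712 = 0.005.

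| Signal | Candidates | Deaths | N=500 | N=1000 | N=2000 | N=5000 |
|---|---|---|---|---|---|---|
| Moderate | 25 | 35% | 0.027 | 0.011 | 0.006 | 0.003 |
| Moderate | 25 | 20% | 0.045 | 0.018 | 0.009 | 0.005 |
| Moderate | 25 | 10% | 0.082 | 0.034 | 0.019 | 0.008 |
| Moderate | 50 | 35% | 0.044 | 0.021 | 0.011 | 0.005 |
| Moderate | 50 | 20% | 0.068 | 0.034 | 0.016 | 0.006 |
| Moderate | 50 | 10% | 0.120 | 0.064 | 0.035 | 0.015 |
| Weak | 50 | 20% | not run | 0.069 | 0.035 | 0.019 |
| Weak | 50 | 10% | not run | not run | 0.071 | 0.029 |

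The Monte Carlo SE is about 0.002-0.004, so the smallest values at 5000 are barely distinguishable from zero. A separate run with 25 candidates, 27% deaths and exit at p 0.10 gave 0.050, 0.012 and 0.004 at n=300, 1000 and 5000.

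**Step 2: deaths are the better scale.** With 25 candidates, 200 deaths give 0.018 (1000 x 20%) or 0.019 (2000 x 10%). With 50 candidates, 350 deaths (1000 x 35%) give 0.021 and 400 (2000 x 20%) give 0.016. With moderate signal, optimism of 0.02 is therefore reached near 200 deaths with 25 candidates and near 350-400 with 50.

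**Step 3: the stopping rule matters.** At N=1000, 50 candidates and 20% deaths, exit at p 0.05, 0.10 or 0.157 (AIC) gives 0.023, 0.034 or 0.041.

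**Step 4: one model or two.** Another simulation used 25 candidates (20 null) and 27% deaths at 12 weeks. It compared the variable set from the stated stepwise rule with the set from a second elimination, at n=300 / 1000 / 5000. The sets differed in 26% / 8% / 0% of studies if the second rule is also p<0.10, 71% / 68% / 75% if AIC, and 80% / 67% / 58% if p<0.05.

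**Step 5: effect of the correction.** In the same setting with AIC elimination and 150 resamples, repeating the selection in each resample moved the mean error from 0.058 to -0.005 at n=300 and from 0.015 to -0.008 at n=1000. Coverage of the 95% c-index interval (SE 2-5 points):

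| Interval | n=300 | n=1000 |
|---|---|---|
| Uncorrected, model held fixed | 42% | 87% |
| Uncorrected, selection repeated | 4% | 47% |
| Fixed-model interval shifted by the optimism | 86% | 90% |

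This part was not run at 5000.

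**Step 6: one c-index per variable.** For retained variables with log-HR of 0.3 or more, the overstatement was 0.002 / 0.000 / 0.001 at n=300 / 1000 / 5000. For weak or null variables reported because they were retained, it was 0.043 / 0.020 / 0.008.

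**The case against.** The strongest reply is that the study is descriptive, neither endpoint names a c-index, and at 5000 patients with a moderate death rate the overstatement is 0.003-0.006. That size stands for those assumptions. But section 5.2 itself plans to report predictive accuracy after selection, 5000 is a ceiling, and the documents do not fix the conditions under which the bias is negligible.

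The two paragraphs can also be read as one procedure with the p thresholds carried over. That is fair: no discrepancy between models is demonstrated, and the high percentages in step 4 need a rule that the documents do not state. The text does not say it is one procedure either. Naming a package does not settle which c-index is reported. The wording about each candidate variable may mean one c-index per variable, in which case strong factors are not materially overstated.

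A reader might infer more than the documents support:

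- *That the bias matters only below some fixed number of patients, such as 1000-2000.* No such limit holds. Few deaths, more candidates or weak predictors keep it at about 0.015-0.03 at 5000.
- *That the cohort will be small.* The three-month window and single centre make this possible, but section 7.5 points to several trusts and no expected accrual is given.
- *That the stepwise model must give way to a full pre-listed model because its hazard ratio intervals cover poorly.* Coverage of 72% for retained terms against 93% for all terms of a full model at n=300 is not like for like. Among full-model terms with p<0.10 it was 76%, against 75% for retained terms. Null factors whose interval excludes 1 are about as frequent either way (1.43 full against 1.47 selected per study at n=300).

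**Conclusion.** The point holds for the multivariable c-index: as written, it would be reported too high, by an amount the documents do not allow one to fix. With moderate signal, 25 candidates and 20-35% deaths the excess is about 0.03-0.05 at 500 patients, 0.01-0.02 at 1000 and 0.003-0.005 at 5000. It matters most if the obtained cohort falls well below the ceiling, which is possible but not established. All sizes rest on assumed effects, death rates and candidate counts.

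The missing stopping rule, the relation between the two paragraphs, and which c-index is meant are matters for clarification. The text suggests that treatment type and infection features stay in the model, but does not say that they are exempt from elimination. Unadjusted hazard ratios and Kaplan-Meier medians are not affected.

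**What to change.** Amend section 5.2 as follows.

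1. Use one backward elimination, with one stated stopping rule, for both the adjusted hazard ratios and the c-index. Keep anticancer treatment type and SARS-CoV-2 features in the model, as the text implies.
2. Repeat the whole elimination in each of the 150 planned resamples. In each, take the c-index of the resample's model in the resample minus its c-index in the original data. The mean difference, O, is the optimism.
3. Report the apparent c-index minus O. For the interval, hold the selected model fixed, take the percentile limits, and subtract O from both. Do not use uncorrected limits from resamples that re-select, which had the worst coverage.
4. State the numbers of deaths and candidate parameters beside the result.
5. If one c-index per variable is meant, say so and report it for every candidate, not only the retained ones.

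The cost is a little more computing and a slightly lower reported c-index; no new data are needed. The correction may overshoot slightly (about -0.005 to -0.008 in the simulation), and the shifted interval stays somewhat below nominal coverage (86-90%). At n=1000 its gain over the uncorrected fixed-model interval is within simulation error. The change should not be presented as improving hazard ratio coverage or reducing false-positive factors.
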